## 6.2 ONC201 Dose Adjustments

The descriptions and grading scales found in the revised NCI CTCAE v5.0 will be utilized for dose delays and dose modifications

Criteria for disrupting treatment, dose modification, or discontinuation are listed in **Table 5**.

For subjects who do not tolerate the dosing schedule, dose adjustments are permitted in order to allow the subject to continue the study treatment.

Below are dose modifications (**Table 5**) for adverse events that are at least possibly, probably or definitely attributable to study drug, including: nausea, vomiting, diarrhea, neutropenia, and thrombocytopenia. If a patient experiences other adverse

events, or several adverse events and there are conflicting recommendations based on grade, the investigator will use the recommended dose adjustment that reduces the dose. Dose modifications will be made based on an adverse event that occurs any time during a cycle.

**Table 5: Dose adjustment rules for Adverse Events (AEs),** including nausea, diarrhea, neutropenia, thrombocytopenia, and other AEs. Alopecia does not require dose adjustments. Lymphopenia does not require dose adjustment unless clinically significant per treating physician.

CTCAE Grade	Management/Next Dose for ONC201
≤ Grade 2	No change in dose
Grade 3 or 4*	Hold until ≤ Grade 2. If resolved to ≤ Grade 2 within 7 days, resume dosing at 500mg if previously dosed at 625mg or resume dosing at 375mg if previously dosed at 500mg.** (See monitoring guidelines below)

\*Patients requiring a delay of ONC201 for >3 weeks must go off protocol therapy.  
Patients with grade 3 neutropenia associated with fever must also discontinue ONC201.  
\*\*Patients requiring > two dose reductions must discontinue ONC201.

Participants who experience an adverse event that requires a treatment delay or dose reduction should be monitored with appropriate laboratory testing or other clinical evaluation at least weekly until resolution; if the adverse event does not resolve within 3 weeks, the interval for testing may be reduced after consultation and written approval by the study PI.

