#### **Neutropenia and Neutropenic fever and other cytopenias:**

Subjects with neutropenic fever or infection should be evaluated promptly and treated with IV antibiotic therapy or therapeutic colony-stimulating factors as appropriate following the ASCO guidelines. Packed red blood cell and platelet transfusion should be administered as clinically indicated.

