**Table 3: Dose adjustment rules for Adverse Events (in addition to Table 5 below)**

CTCAE Grade	Management for the methionine-restricted diet
Weight loss	
Grade 2 or higher	Methionine restricted diet must be discontinued.
Homocysteine levels (to be captured as: Metabolism and Nutrition disorders – other, specify)	
Grade 2 or higher	Methionine restricted diet must be discontinued

Normal homocysteine levels are 5-15 micro mol/L.

For purposes of this study homocysteine levels will be graded per the table below:

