### **6.3 Protocol therapy discontinuation**

In addition to discontinuation from therapy related to toxicities as outlined in section 6.1, a subject will also be discontinued from protocol therapy and followed up per protocol under the following circumstances:

- Documented disease progression
- Discontinue methionine restricted diet for weight loss grade 2 or higher
- The treating physician thinks a change of therapy would be in the best interest of the subject
- The subject requests to discontinue protocol therapy, whether due to unacceptable toxicity or for other reasons
  - If a subject decides to prematurely discontinue protocol therapy ("refuses treatment"), the subject should be asked if he or she may still be

contacted for further scheduled study assessments. The outcome of that discussion should be documented in the medical records.

- A female subject becomes pregnant
- If protocol therapy is interrupted for >21 days.

Subjects will be removed from protocol therapy, and the site investigator notified, when any of the criteria listed above apply. The reason for discontinuation of protocol therapy will be documented on the eCRF in OnCore.

Subjects who discontinue protocol therapy will be followed every 3 months for 2 years after the end of treatment visit. Survival status and anti-cancer therapy (to include only first cancer directed therapy after study) will be collected from review of medical records or via telephone follow up.

If subjects discontinue study treatment prior to disease progression, scans during follow-up will be completed per standard of care, but RECIST measurements must be completed until disease progression or start of new anti-cancer therapy.

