## **12.3 Review and Oversight Requirements**

### **12.3.1 Serious Adverse Event – Reported within 24 Hours**

Serious Adverse Events requiring reporting within 24 hours (as described in the protocol) must also be reported to the Data and Safety Monitoring Committee (DSMC) Chair via an email to [[contact]](mailto:[contact]) within one business day. The OnCore SAE Details Report must be submitted along with other report materials as appropriate (NCI AdEERS form or FDA Medwatch Form #3500 and/or any other documentation available at that time of initial reporting). The DSMC Chair will review the information and determine if immediate action is required. Within 5 calendar days, all available subsequent SAE documentation must be submitted electronically along with a 24-hour follow-up SAE Details Report and a completed UWCCC SAE Routing Form to [[contact]](mailto:[contact]). All information is entered and tracked in the UWCCC database.

The Principal Investigator notifies all investigators involved with the study at the UWCCC, the IRB, the sponsor, and the funding agency and provides documentation of these notifications to the DSMC. If the SAE occurs on a clinical trial in which the UW PI serves as the sponsor-investigator, the PI reviews the event to determine whether the SAE requires reporting to the FDA and other participating investigators. For a multiple-institutional clinical trial the PI is responsible for ensuring SAEs are reported to the FDA as well as to all participating investigators.

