**FDA Reporting Requirements for Serious Adverse Events (21 CFR Part 312)**

**NOTE:** Investigators **MUST** immediately report to the University of Wisconsin Carbone Cancer Center and any other parties outlined in the protocol ANY Serious Adverse Events, whether or not they are considered related to the investigational agent(s)/intervention (21 CFR 312.64).

An adverse event is considered serious if it results in ANY of the following outcomes:

- 1) Death.

- 2) A life-threatening adverse event (the patient was at risk of death at the time of the event; it does not refer to an event that hypothetically might have caused death if it were more severe).
- 3) An adverse event that results in inpatient hospitalization or prolongation of existing hospitalization for  $\geq 24$  hours.
- 4) A persistent or significant incapacity or substantial disruption of the ability to conduct normal life functions.
- 5) A congenital anomaly/birth defect.
- 6) Important Medical Events (IME) that may not result in death, be life threatening, or require hospitalization may be considered serious when, based upon medical judgment, they may jeopardize the patient or subject and may require medical or surgical intervention to prevent one of the outcomes listed in this definition (FDA, 21 CFR 312.32; ICH E2A and ICH E6).

**ALL SERIOUS** adverse events that meet the above criteria **MUST** be immediately reported to the UWCCC within the timeframes detailed in the table below:

Hospitalization	Grade 1 and Grade 2 Timeframes	Grade 3-5 Timeframes
Resulting in hospitalization <math>\geq 24</math> hrs	10 Calendar Days	24 Hour; 5 Calendar Days
Not resulting in Hospitalization <math>\geq 24</math> hrs	Not required	

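### The Table 5 footnote in section 6.2 makes Grade 3 neutropenia with fever a mandatory stop of ONC201 but does not name Grade 4, so read literally the more severe event may resume at a lower dose

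*Combined protocol and SAP*

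**What the plan says.** Section 6.2 governs ONC201 after adverse events that are at least possibly attributable to the drug. Table 5 has one row for Grade 3 and Grade 4 together. ONC201 is held until the event is Grade 2 or lower. If that happens within 7 days, the instruction is to "resume dosing at 500mg if previously dosed at 625mg or resume dosing at 375mg if previously dosed at 500mg".

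An asterisk on that row leads to a footnote with two stops. One takes a subject off protocol therapy after a delay of more than 3 weeks. The other reads: "Patients with grade 3 neutropenia associated with fever must also discontinue ONC201". A second footnote stops ONC201 when more than two dose reductions would be needed. Below the table, weekly or more frequent monitoring is called for until an event that led to a delay or reduction has resolved.

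The stops for the diet are worded as floors. Table 3 in section 6.1 uses "Grade 2 or higher" for both weight loss and homocysteine, and section 6.3 repeats the weight-loss rule: "Discontinue methionine restricted diet for weight loss grade 2 or higher".

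**The concern.** The row covers two grades, but the footnote that overrides it for febrile neutropenia names only the lower one. Taken at its word, the protocol requires a permanent stop at Grade 3 with fever and allows a reduced-dose restart at Grade 4 with fever. That reverses the order of severity.

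What is at stake is the consistency of a mandatory safety rule. Section 13.1 describes competitive accrual across sites, so two sites could read the footnote differently and manage the same event in opposite ways, each with support in the text.

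**Working it through.** No arithmetic settles this. The check is to apply the text to each grade, then look for any other section that closes the gap.

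**Step 1: the literal outcome by grade, for neutropenia with fever attributed to ONC201.**

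| Step | Grade 3 with fever | Grade 4 with fever |
|---|---|---|
| Immediate action | ONC201 discontinued (footnote) | ONC201 held (Table 5 row) |
| Recovery to Grade 2 or lower within 7 days | No restart | Restart at 500 mg (from 625) or 375 mg (from 500) |
| Recovery after 7 days but within 3 weeks | No restart | No restart instruction is given |
| Delay of more than 3 weeks | Already stopped | Off protocol therapy |

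The two columns clearly conflict only in the second row: a restart against a permanent stop.

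**Step 2: which subjects fall into that row.**

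- *Dose level.* The steps are 625 to 500 mg (first reduction) and 500 to 375 mg (second). A qualifying event at 375 mg would need a third reduction. Three is more than two, so the second footnote already stops ONC201. The gap is therefore confined to subjects on 625 mg or 500 mg.
- *Timing of fever.* A count recovering from Grade 4 passes through Grade 3. If fever is still present then, the footnote applies as written. The gap remains where the fever resolves first.

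**Step 3: does another section make the stop mandatory at Grade 4?**

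- *Section 5.6, neutropenic fever.* "Subjects with neutropenic fever or infection should be evaluated promptly and treated with IV antibiotic therapy or therapeutic colony-stimulating factors". This directs evaluation and treatment. It states no grade and no action on ONC201.
- *Section 6.2, conflicting recommendations.* The investigator takes the option that lowers the dose. A lower dose is not a stop.
- *Section 6.3.* Febrile neutropenia is not in the list, and the opening reference for toxicity stops is to section 6.1, the diet section. What remains is clinical judgment: "The treating physician thinks a change of therapy would be in the best interest of the subject". That permits a stop and does not require one.
- *Section 11.1.1.* Weekly follow-up for four weeks after an interruption for an adverse event. This is follow-up, not a drug action.
- *Section 12.2.1.* Regular team meetings may discuss toxicities and dose adjustments, with no set outcome for this event.
- *Section 12.3.1.* "The DSMC Chair will review the information and determine if immediate action is required". This is case by case.
- *Section 12.4.* Serious events must "be immediately reported to the UWCCC within the timeframes detailed in the table below", and section 12.4.3 sends reports from network sites to the coordinating investigator and the DSMC Chair. Neither fixes what happens to ONC201.

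None of these extends the mandatory stop to Grade 4.

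**The case against.** The best reply is that context supplies the missing grade. The asterisk sits on a row that names Grade 3 and Grade 4, the footnote adds to that row, and few clinicians would stop at Grade 3 with fever and restart after Grade 4. This largely stands as an account of intent: the omission is probably a slip, and many investigators would apply the stop to both grades. It does not repair the wording. The row names both grades and the footnote names one, which leaves room for the restrictive reading. The comparison with the diet rules helps only a little, because those are free-standing triggers and not a note on a row that already lists the grades.

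A second reply is that the event looks unlikely. Section 1.5.4 reports no drug-related toxicity above Grade 1 among ten phase I patients. That is fair context, but those patients were dosed once every 3 weeks and this trial doses on two days of every week. It sets no rate here, in either direction.

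Two stronger readings are tempting and should not be drawn.

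- *That Grade 4 is left to the physician's discretion.* It is not. The hold, the lower dose on restart, the at-least-weekly monitoring and removal after more than 3 weeks are all written into section 6.2.
- *That the wording decides who is evaluable for response, and so reaches the ORR result.* The documents do not support a firm dose count. The count depends on whether the dose on the day of onset was taken and on how the one-day allowance for late doses in section 5.2 applies to held doses. Beyond 7 days, Table 5 gives no restart instruction to model.

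**Conclusion.** The concern holds as a gap in the wording of a mandatory safety rule. Read literally, Grade 4 neutropenia with fever may restart at a reduced dose after recovery within 7 days, while Grade 3 with fever may not restart at all. The gap is limited to subjects on 625 mg or 500 mg whose fever clears before the count recovers through Grade 3, and the other Grade 4 rules, clinical judgment and serious-event review soften it further.

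It has no effect on the Simon two-stage design in section 13.2 or its error rates, because neither its sample sizes nor its response cut-offs depend on this footnote. The frequency of the event cannot be obtained from the documents. The conclusion rests on the literal text and on the assumption that nothing outside the protocol, such as a procedures manual, supplies the missing grade. It should be corrected because the rule concerns patient safety and the correction is simple.

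**What to change.** In the asterisk footnote to Table 5 of section 6.2, insert *or 4* after *grade 3* in the sentence on neutropenia with fever, so that the stop covers both grades named in the row. If the investigators do intend Grade 4 to be held and restarted, the footnote should say so and give the reason.

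The cost is two words in a protocol amendment, with no added visits, samples or data. The clinical downside is that a rare subject whose Grade 4 event resolves quickly comes off ONC201, as already happens at Grade 3. If this occurs early, the subject may not be evaluable for response and may need to be replaced under section 13.3.

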### **6.3 Protocol therapy discontinuation**

In addition to discontinuation from therapy related to toxicities as outlined in section 6.1, a subject will also be discontinued from protocol therapy and followed up per protocol under the following circumstances:

- Documented disease progression
- Discontinue methionine restricted diet for weight loss grade 2 or higher
- The treating physician thinks a change of therapy would be in the best interest of the subject
- The subject requests to discontinue protocol therapy, whether due to unacceptable toxicity or for other reasons
  - If a subject decides to prematurely discontinue protocol therapy ("refuses treatment"), the subject should be asked if he or she may still be

contacted for further scheduled study assessments. The outcome of that discussion should be documented in the medical records.

- A female subject becomes pregnant
- If protocol therapy is interrupted for >21 days.

Subjects will be removed from protocol therapy, and the site investigator notified, when any of the criteria listed above apply. The reason for discontinuation of protocol therapy will be documented on the eCRF in OnCore.

Subjects who discontinue protocol therapy will be followed every 3 months for 2 years after the end of treatment visit. Survival status and anti-cancer therapy (to include only first cancer directed therapy after study) will be collected from review of medical records or via telephone follow up.

If subjects discontinue study treatment prior to disease progression, scans during follow-up will be completed per standard of care, but RECIST measurements must be completed until disease progression or start of new anti-cancer therapy.

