**2.3 Exploratory Objective:**

2.3.1 To determine time to development of brain metastases or worsening of brain metastases in patients with metastatic TNBC treated with ONC201 with a methionine-restricted diet.

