- (2) Blood will be taken to assess plasma methionine levels at baseline, cycle 2 day 5, then day 5 of every other cycle, and at end of treatment. Subjects must be fasting. If necessary, these labs may be drawn as early as day 2, but prefer to be as close to day 5 as possible without going over.
- (3) If clinically indicated.
- (4) Optional biopsy prior to study entry.
- (5) Blood for circulating tumor cells will be taken at baseline, day 5 of cycle 2, and at end of treatment. If necessary, these labs may be drawn as early as day 2, but prefer to be as close to day 5 as possible without going over.
- (6) For women of childbearing potential. To be completed within 7 days of randomization. Must be repeated at cycle 1 day 1 if not completed in previous 7 days.
- (7) Subjects whose treatment is interrupted or permanently discontinued due to an adverse event (including lab values) should be followed per section 11.1.1.
- (8) Waist circumference, optional if not possible due to site limitations. Not required at screening.
- (9) CMP to include sodium, potassium, chloride, carbon dioxide, glucose, BUN, creatinine, calcium, albumin, total protein, alkaline phosphatase, aspartate aminotransferase (AST), alanine aminotransferase (ALT), and total bilirubin.
- (10) CT chest with or without contrast and CT with contrast or MRI of Abdomen/Pelvis to be completed during screening and  $\leq$  7 days prior to every third cycle starting at cycle four (approximately every 9 weeks; e.g. cycles 4, 7, 10, etc.). If subjects discontinue study treatment prior to disease progression, scans during follow-up will be completed per standard of care, but RECIST measurements must be completed until disease progression or start of new anti-cancer therapy.
- (11) Homocysteine/cysteine level at: baseline and every 3 cycles while on study (C1, C4, C7, etc.) and at end of treatment.
- (12) One block or 10 unstained slides.
- (13) labs/physical exam/ECOG PS does not need to be repeated if done within 7 days prior to C1D1

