### 13.7.3 Analysis plans for exploratory objectives

Kaplan-Meier methodology will be used to summarize time-to-event data, such as time to development of brain metastases or worsening of brain metastases in patients with metastatic TNBC treated with ONC-201 with a methionine-restricted diet. Graphical techniques (e.g., waterfall plots, KM curves, line plots) may be used when such methods are appropriate and informative.

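### Brain metastases arising after first progression or after new anti-cancer therapy are not listed for collection, and the time-to-brain-metastases analysis has no censoring rule

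*Combined protocol and SAP*

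**What the plan says.** Section 2.3 sets the exploratory objective: "To determine time to development of brain metastases or worsening of brain metastases in patients with metastatic TNBC" given the combination. It names no time window and no end at progression or at the end of treatment.

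Section 13.7.3 supplies the analysis: "Kaplan-Meier methodology will be used to summarize time-to-event data, such as time to development of brain metastases or worsening of brain metastases". It gives no time origin, censoring rule or treatment of death.

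On follow-up, section 6.3 takes subjects off therapy at documented progression, among other reasons, and then states: "Subjects who discontinue protocol therapy will be followed every 3 months for 2 years after the end of treatment visit". The items for all subjects are these: "Survival status and anti-cancer therapy (to include only first cancer directed therapy after study) will be collected from review of medical records" or by telephone.

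Subjects who stop before progression have one further provision. Scans follow standard of care, and "RECIST measurements must be completed until disease progression or start of new anti-cancer therapy". Footnote 10 of the section 7 calendar repeats this.

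The Long-term Follow-up column of the calendar marks only body CT/MRI and survival. Brain MRI has a single mark, at screening, if clinically indicated. Under section 11.2.1, adverse events are recorded until 30 days after study drug stops.

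**The concern.** Take a subject who leaves therapy because of extracranial progression and is found to have brain metastases some months later. Staff are already reviewing her record or telephoning every 3 months, yet nothing in section 6.3 or the calendar asks them to record the brain diagnosis or its date. The same holds for a subject who stops before progression, starts another therapy and then develops brain disease.

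The objective reads as open-ended, but data collection supports it only up to about first progression. Two things are at stake. In a trial of at most 34 subjects the number of brain events will be small, and some would be lost although the contacts that could capture them are already planned. Observation would also end for many subjects just as their disease worsens, so censoring may be related to brain risk. With no written rule in 13.7.3, the analyst would have to choose a censoring date after the data are in.

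**Working it through.** The plan gives no figure for the brain endpoint. The check is first a reading of what is collected when, then an illustration of size.

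**1. What is collected, by period**

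| Period | Named collection | Would a brain event be recorded? |
|---|---|---|
| On treatment to end-of-treatment visit (35 days after last dose) | Clinic visits, AEs, body imaging about every 9 weeks | Yes, if clinically detected |
| Stopped before progression, until progression or new therapy | Standard-of-care scans, RECIST measurement, survival, first next therapy | Yes, if found; a new lesion is progression (sections 9.5-9.7) |
| After progression or new therapy, up to 2 years | Survival, first next therapy | Not listed |

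The gap is the third row.

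**2. Follow-up time without brain information**

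Inputs: median survival 13 months (section 1.1); visit at 35 days = 1.15 months (section 7); 24 months of later follow-up (section 6.3). Assumptions, not in the documents: exponential times and median treatment time T = 2, 4 or 6 months.

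Let A be time on treatment (mean T/ln 2) and P survival after treatment, exponential with mean m chosen so that A + P has median 13 months (m is about 14.2, 10.0 and 6.9).

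- Time with brain information = E[A] + m(1 − exp(−1.15/m))
- Total follow-up = E[A] + m(1 − exp(−25.15/m))

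For T = 2: 2.9 + 1.1 = 4.0 months, against 2.9 + 11.8 = 14.7 months. Unobserved share = 1 − 4.0/14.7 = 73%.

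| Median time on treatment | With information | Total | Unobserved |
|---|---|---|---|
| 2 months | 4.0 | 14.7 | 73% |
| 4 months | 6.8 | 14.9 | 54% |
| 6 months | 9.7 | 15.4 | 37% |

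Two adjustments, each applied separately:

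- If 30% stop before progression and keep RECIST measurement for a further median of 2 months (assumed), the shares are 68%, 50% and 34%.
- With uniform accrual over 30 months and a cut-off at 36 months (the Synopsis estimates), they are 67%, 47% and 31%.

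**3. Events, at an assumed 0.2 brain events per year**

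Expected events = 34 × E[1 − exp(−0.2t/12)], with t in months. This gives 2.1, 3.5 and 4.8 recorded for T = 2, 4 and 6, against about 7 with capture at the follow-up contacts (about 6 under the 36-month cut-off).

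**4. A second method: constant competing hazards**

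Death hazard h_d = ln 2/13 = 0.0533 per month. If a share c has a brain event before death, h_b = c·h_d/(1 − c), and the share with an on-treatment event is h_b/(h_b + ln 2/T).

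For c = 0.2 and T = 4: h_b = 0.0133; 0.0133/(0.0133 + 0.1733) = 0.071; 34 × 0.071 = 2.4 of 34 × 0.2 = 6.8 events. So 1 − 2.4/6.8, about 64%, fall after treatment.

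Over c = 0.1 to 0.3 the share is 79-83%, 61-67% and 45-51% for T = 2, 4 and 6. This is an upper bound on the loss, because it credits no capture after treatment, neither up to the 35-day visit nor through RECIST follow-up.

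**5. Direction of any bias**

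In steps 2 and 3 the brain rate does not depend on progression, so the censoring is non-informative. The 12-month brain-event-free Kaplan-Meier estimate is exp(−0.2) = 0.82 whether observation ends at the 35-day visit or continues. The model shows lost events and precision, not bias.

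**The case against.** A reader might infer that follow-up records nothing beyond survival and next therapy, so that no brain metastasis is ever counted once treatment stops. The documents do not support that. Section 6.3 lists several reasons for stopping other than progression, and those subjects keep RECIST measurement until progression or new therapy. A brain lesion found as their first progression would be captured. The route is narrow, since imaging is standard of care and no brain MRI is scheduled after screening, but it exists.

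A reader might also infer that the endpoint is censored at treatment stop. No such rule is written; the defect is that there is none.

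Section 15.2 says selected standard-of-care data will be captured according to study objectives, and the case report forms are not in the file. That sentence concerns procedures on the study calendar, however, and names no CNS item for follow-up. Brain radiotherapy might appear as the first next therapy, but only incidentally and without a diagnosis date.

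The strongest remaining argument is that ending observation near progression is a legitimate choice: the objective concerns patients treated with the combination, and later brain events also reflect next-line therapy. That stands as a possible estimand, but neither 2.3 nor 13.7.3 states it. It is also fair that the size rests on assumed rates and treatment times, that all 34 subjects may not enrol (at a true ORR of 0.10 the two-stage design stops after 13 with probability 0.62), and that no decision depends on this endpoint.

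**Conclusion.** The gap holds in a limited form. Brain metastases that develop or worsen after first progression, or after new anti-cancer therapy starts, are not listed for collection, and 13.7.3 has no censoring rule. Observation therefore ends in practice at about first progression, new therapy or the end-of-treatment visit.

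The share lost is likely to be substantial but cannot be derived from the documents, which give neither a brain-event rate nor a time on treatment. As an illustration only, roughly 30-70% of follow-up time would be uninformative for median treatment times of 2 to 6 months.

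It is tempting to add that the curve would look too favourable. That is not established. If brain risk rises after progression, censoring there would push the curve in that direction. Treating death as ordinary censoring would push estimated incidence the other way. The net effect is unknown.

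The endpoint is exploratory and the ORR conclusion is unaffected. This is a cheap improvement, worth making before follow-up data are lost.

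**What to change.** - **Section 6.3 and the Long-term Follow-up column:** add two items to the existing 3-monthly record review or telephone contact, namely the date of first diagnosis or worsening of brain metastases and the date of last known CNS status.
- **Section 13.7.3:** measure from treatment initiation; count brain events whether or not the subject is still on protocol therapy; censor at the last known CNS-status date; treat death without a brain event as a competing event and report cumulative incidence. Add a sensitivity analysis that ends observation at progression or new therapy.
- **Alternative:** if the sponsor wants only events up to progression or new therapy, state that in 2.3 and 13.7.3.

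The cost is two form fields and a few sentences of analysis text, with no extra scan. The downsides are that later events may reflect next-line therapy, as they do for OS, and that detection without scheduled brain imaging is clinical. The report should say both.
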